We will compare the two strategies overall (1°) and for each stage of the contact investigation cascade (2°), as well as yield of diagnoses/treatments for active and latent TB (2°). We will construct multilevel logistic models (or Poisson models for counts), adjusted for clustering within clinics/communities and within index patient clusters, to estimate proportions (or counts) with exact binomial 95% confidence intervals. We will compare primary outcomes between control and intervention periods using adjusted chi-squared tests of proportion. We will determine and report ICC at both health centre and index patient levels. We will fit a multilevel, generalized linear mixed-effects model with a logit link and random effects for clustering and fixed effects for step (*i.e.*, point in time). For sustainability we will analyze the interaction between intervention and time-elapsed-since-intervention-initiation to determine if the intervention effect strengthens or weakens over time as it becomes routinized, looking at both TB evaluation and diagnosis. We will also explore variation in delivery processes and outcomes for the following:

- (1) Health facility clusters,
- (2) Community health workers, and
- (3) Clinically important sub-groups including women, men, younger children (age<5), older children (age 5-14), adults, and PLHIV, all in pre-specified sub-group analyses.

There is a strong biological rationale for each of these analyses, given known differences in TB diagnostic performance by sex and in WHO recommendations for TB evaluation by age and HIV status.

We will prepare flow and cascade diagrams to illustrate key contact investigation process measures, as in our previously published work. We will produce time-series graphs demonstrating change in cumulative likelihood of completion of contact investigation and each of the component process measures over time. We will prepare tables describing associations between provider and clinic characteristics and likelihood of completion, stratified by key individual- and household-level characteristics of community members. Tests of significance will be applied as needed at the adjusted $p<0.05$ level.

Primary Outcomes

1. Referred contacts completing TB evaluation
 - a) Count (Number of contacts who complete TB evaluation within 60 days of index patient diagnosis)

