Statistical Analysis Plan: HCD-CoP Study

NCT05640648

Trial Title	A User-Centered Strategy to Improve Delivery of TB Contact Investigation in Uganda: A Stepped-Wedge Cluster Randomized Implementation Trial
Grant Title	Human-centered Design and Communities of Practice to Improve Delivery of Home-based TB Contact Investigation in Uganda
Grant Acronym	HCD-CoP
Trial Registration	ClinicalTrials.org
Principal Investigators	[name], [name]
Date	May 2, 2023

I. Introduction

1. Study Aims

Primary Objective

Aim 1: To compare the implementation, effectiveness, and public health impact of a user-centered strategy versus the standard strategy for implementation of TB contact investigation in a stepped-wedge, cluster-randomized implementation trial.

- **User-centered Strategy:** Training + Supportive Supervision + Electronic Data Collection + Facilitation Tools + Communities of Practice
- **Standard Strategy:** Training + Supportive Supervision + Electronic Data Collection

Secondary Objectives

Aim 2: To identify processes and contextual factors that influence the implementation, effectiveness, and public health impact of the user-centered contact investigation strategy.

Aim 3: To compare the costs and epidemiological impact of the user-centered and standard implementation strategies for TB contact investigation.

Overview

This statistical analysis plan covers the primary objectives of assessing the implementation and key secondary effectiveness and public health impact outcomes. **This document will not further address the trial's secondary objectives of assessing implementation fidelity and context (Aim 2) and implementation costs and impact at scale (Aim 3).** Study endpoints will be evaluated through a review of data entered into the HCD-CoP CommCare (Dimagi, Boston, MA) database by community health workers as part of their routine TB contact investigation activities, with validation of effectiveness endpoints using source data entered into Uganda National TB and Leprosy Programme TB treatment registers for all patients initiating TB treatment at participating health facilities. Trial results reporting will follow the CONSORT 2010 statement extension for stepped-wedge trials (**SWT**).^[1, 2] This statistical analysis plan is written in support of and is entirely consistent with the full trial protocol; however, in case of any discrepancies, this statistical analysis plan takes precedence.

1. Trial Summary

Trial Design

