The study proposes to conduct a stepped-wedge, cluster-randomized implementation trial of a novel, user-centered implementation strategy for the delivery of TB contact investigation at 12 TB diagnostic and treatment units (DTUs) located at health facilities in central Uganda. The trial over will proceed over the course of 16 trial steps, each 8 weeks in duration, with the intervention period lasting from as little as 16 weeks up to 56 weeks at the participating facilities. We will use a complete stepped-wedge design, including an 8-week transition period for training and initial adoption, followed by 8 to 52 weeks of post-intervention data collection at each site. Data collected during the transition periods will not be included in the final analysis. In addition, the trial will be paused for 6 weeks during the annual 2022-2023 year-end holiday period (12 December 2022 through 15 January 2023; all transition periods falling during and after this pause period will be delayed by six weeks and patients recruited during this period, as well as the data of their contacts, will be excluded from the trial.[§] The rationale for this pause is that staffing levels and patient visits are low during this period, and without exclusion, this could bias the trial results in uncertain ways.

§Version 2.0 Update: On 15 October 2022, the President of Uganda announced Ebola-related public health restrictions preventing public movement in two districts where two study sites are located: Mubende and Kasambya. As a result, the principal investigators immediately paused all new introductions of the study intervention effective immediately for the subsequent 8-week period ending 11 December 2022, effectively extending the previously proposed 6-week study pause by at least 14 weeks. The original schema is shown below in Figure 1, and an updated schema is shown below in Figure 2.

[figure not shown]

Figure 1. HCD-CoP Intervention Randomization and Enrolment Schedule.

Legend: Ordinal numbers indicate the cross-over sequence from standard to the intervention period. Note that pause periods are not shown in the current figure.

Group	Site	Month																	
		1 Mar 7 - Apr 3	2 Apr 4 - May 1	3 May 2 - May 29	4 May 30 - Jun 26	5 Jun 27 - Jul 24	6 Jul 25 - Aug 21	7 Aug 22 - Sep 18	8 Sep 19 - Oct 16	9 Oct 17 - Nov 13	10 Nov 14 - Dec 11	Holiday	11 Dec 12 - Jan 15	12 Jan 16 - Feb 12	13 Feb 13 - Mar 12	14 Mar 13 - Apr 9	15 Apr 10 - May 7	16 May 8 - Jun 4	17 Jun 5 - Jul 2

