This sequence of allocation restricted by sites will be determined through a two-stage random drawing during a public randomization ceremony held in Kampala, Uganda. A senior clinician representative of each health center (e.g., the TB focal person), the Health Facility Administrator-in-Charge, and the District Health Officer will be invited to attend a public randomization ceremony chaired by the Uganda NTLP Director. In the first, so-called “Cluster Stage”, health facilities will be divided into high-volume and low-volume strata for cluster assignments. Each health center representative will draw, without replacement, one ball labeled with the cluster designation, until all sites are assigned in paired clusters. In the second and final, or “Group Stage,” the two representatives of each cluster will assign one representative to draw, without replacement, 1 of 6 balls (labeled 1, 2, 3, 4, 5, 6) from an opaque bag to choose the group. Group 1 will be the first group to cross over, Group 2 the second to cross over, and so on. The sites will follow this cross-over sequence at equally spaced, 2-month intervals during the trial period, starting at the beginning of month 3.

Statistical Methods

For standardization purposes, the start of effective intervention exposure for clusters will be considered the first Monday of the next calendar week after the end of each 8-week transition period. This standardization will help fix the trial period slices and improve statistical efficiency for the within-period analyses. We will use a cluster-period mixed-effects logit model[5, 6] to assess differences between post-intervention and pre-intervention periods with regard to the proportion of contacts who completed TB evaluation within 60 days of index treatment initiation, the proportion of contacts diagnosed with active TB, the proportion of contacts initiating TB preventative therapy and proportion of all TB cases among contacts. We will use a cluster-period mixed-effects Poisson model[5, 6] to assess the difference between post-intervention and pre-intervention periods with regard to the count of contacts diagnosed with active TB and the count of contacts initiated on TB preventative therapy within and between periods. We will test for secular trends using both fixed and random effects. If secular trends are present, we will use a segmented regression model.

a. Dataset assembly, cleaning, and creation of new variables

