where y_{ijk} is the outcome of individual k in period j from clinic i , μ is the mean outcome in the first period, β_j is the difference between period j and the first period with $\beta_1=0$, θ is the intervention effect, X_{ij} is 1 if cluster i received the intervention in period j and 0 otherwise, u_i is a random effect for cluster, and e_{ijk} is the within-cluster variability.

In a stepped wedge trial, the outcomes will be aggregated at cluster level hence the general model form will be

$$Y_t = \mu + \beta_j + \theta X_{ij} + u_i + e_{ijk}, \dots \quad \text{Equation 2}$$

where Y_t = aggregated outcome within each time slice t , calculated from Y_{ijk} (for i exposure, j period (month) and cluster k). We will adjust for unbalanced time-independent variables at baseline and confounders. The proportion of the outcome variable will be calculated for each site and cluster for each study time-exposure slice.

For between-period (horizontal) comparisons, comparative analysis is done at cluster level hence the general model form is:

$$\text{logit}(Y_{jt}) = \alpha + \beta x_{jt} + \sum \gamma_t z_t + u_j \dots \quad \text{Equation 3}$$

where j indexes the clusters, t indexes the steps, x_{jt} indicates a cluster and exposure; is coded 0 when the j th cluster is in pre-intervention (control) exposure and 1 when it is in the post-intervention (intervention); β represents the intervention effect, γ_t represents the time-specific effects, z_t the steps and u_j represents the cluster-level random effects (within-cluster correlation).

Within-period (vertical) comparisons are done by fitting a model as in Equation 4

$$\text{logit}(Y_{jt}) = \alpha + \beta x_{jt} + \sum \gamma_t z_t + u_j \dots \quad \text{Equation 4}$$

- where x_{jt} indicates a cluster and time and is coded 0 for clusters in pre-intervention (control) exposure and 1 for clusters in the post-intervention (intervention); β represents the intervention effect, and γ_t represents the time vertical slices.

Alternative Statistical analyses[§]

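### The protocol's analysis of whether the effect changes with time since introduction is not carried into the SAP, whose models assume one constant effect

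*SAP*

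**What the plan says.** Protocol section 13 (Statistical Considerations) states: "For sustainability we will analyze the interaction between intervention and time-elapsed-since-intervention-initiation to determine if the intervention effect strengthens or weakens over time". It names TB evaluation and diagnosis as the outcomes for this analysis.

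The SAP's outcome list covers implementation, effectiveness, public health impact, efficiency, timeliness and equity. Sustainability is not among them, and no interaction with exposure time appears. The SAP's Overview sets aside only Aims 2 and 3, describes the SAP as consistent with the protocol, and adds that "in case of any discrepancies, this statistical analysis plan takes precedence".

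Under Intervention Effect Analysis, Equations 1 and 2 carry one coefficient, theta, on an indicator that is 1 if the cluster "received the intervention in period j and 0 otherwise". Equations 3 and 4 also have a single coefficient plus calendar terms; for Equation 3 the SAP explains that "β represents the intervention effect, γ_t represents the time-specific effects".

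Length of exposure varies by design. The SAP's Trial Design section describes the trial "with the intervention period lasting from as little as 16 weeks up to 56 weeks at the participating facilities".

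**The concern.** The strategy is continuous quality improvement. The SAP describes weekly meetings that close by setting improvement objectives, and monthly audit and feedback reports. An effect that builds with use is plausible, and so is one that fades. The protocol raises the question itself when it plans "to determine if the intervention effect strengthens or weakens over time as it becomes routinized".

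Two things are at stake. An analyst who follows the SAP would not run the planned analysis. In addition, once calendar-period effects are in a stepped-wedge model, a single exposure coefficient need not be an average of the effects at different exposure times. An effect that grows could be understated, and one that fades could be overstated and read as lasting.

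**Working it through.** **Does other SAP text supply the missing term?** No.
- Statistical Methods: "If secular trends are present, we will use a segmented regression model". This is conditional on secular trends, and no terms are given.
- Dataset assembly creates exposure-by-month and exposure-by-time-by-cluster variables, but neither enters an equation. The period-specific effect there is unadjusted.
- Random-slope models are named before Equation 1, but the equations contain only a random intercept.
- The alternative models, added after the Ebola restrictions, compare control with intervention only.

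**Inputs.** From the SAP's power section: 12 clinics in 6 pairs, rho = 0.172, and 11 index patients per clinic-block with 1 symptomatic contact each, so n = 11. Each clinic's 8-week transition is excluded (Trial Design).

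The layout used is eight 8-week blocks: one baseline block, transitions in blocks 2 to 7, and at least one later block for every group. This fits the protocol's 16-month period. Group 1 has 56 - 8 = 48 post-transition weeks, or six blocks. The SAP also gives 52 weeks as the maximum.

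**The plan's own figure first.** N = m x g x T x K = 1 x 11 x 7 x 12 = 924, as stated. On the SAP's seven-period layout, the model below with average binomial variance gives a standard error of 0.0465 for 0.20 against 0.40. Power is then Phi(0.20/0.0465 - 1.96) = Phi(2.34) = 0.99, matching the stated 99%. (Table 2 prints 1.0000, which is reproduced only with a control-proportion variance and a residual scaled by 1 - rho2.)

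**Weights.** For clinic-block means, Y = mu + beta_j + theta X_ij + u_i + e_ij, with var(u) = rho and var(e) = (1 - rho)/n on a unit total variance. The generalized least squares estimate of theta is the last row of (X'V^-1 X)^-1 X'V^-1 applied to Y. The weight on exposure block s is the sum of that row over all cells in block s.

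| Exposure block | 1 | 2 | 3 | 4 | 5 | 6 |
|---|---|---|---|---|---|---|
| Groups observed | 6 | 5 | 4 | 3 | 2 | 1 |
| Weight | 0.838 | 0.413 | 0.105 | -0.085 | -0.158 | -0.113 |
| Assumed rising effect (points) | 10 | 14 | 18 | 22 | 26 | 30 |
| Assumed falling effect (points) | 30 | 26 | 22 | 18 | 14 | 10 |

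The weights sum to 1, so a constant effect is recovered exactly.

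**Expected estimates.**
- Rising: 8.38 + 5.78 + 1.89 - 1.87 - 4.11 - 3.39 = 6.7.
- Falling: 25.14 + 10.74 + 2.31 - 1.53 - 2.21 - 1.13 = 33.3.

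**Benchmarks.** Averaged over observed intervention cells, the rising effect is (6x10 + 5x14 + 4x18 + 3x22 + 2x26 + 1x30)/21 = 350/21 = 16.7. The falling effect is 490/21 = 23.3. With equal block weights both are 20. Against the observed-cell average the error is about 10 points either way.

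**Sensitivity.**
- Rho 0.043 (the protocol's value): the rising case gives 8.4.
- n = 22.7 (the SAP's pre-trial index volume, taken as contacts): 6.4. More data do not remove the bias.
- Pause delays groups 4 to 6 by one block and every group keeps at least one post-transition block (nine blocks, with the 10-to-30 profile spread over seven exposure blocks): 7.3 rising and 32.7 falling.

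**Which remedy recovers the truth?** Six block indicators return 10, 14, 18, 22, 26 and 30. A linear term also returns an average of 20.0 here, because the assumed profile is linear. Pooling blocks 3 and later returns 7.62, 11.04 and 16.94, so the block-weighted average is (7.62 + 11.04 + 4 x 16.94)/6 = 14.4, against 20.

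**The case against.** Four points on the other side deserve weight.

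- **Status of the analysis.** A reader might infer that the SAP cancels a trial objective. The documents do not support that. Sustainability is an analysis in protocol section 13. It is not part of the Phase 2 objective or among the listed primary and secondary outcomes. The SAP says it covers primary and key secondary outcomes, and its precedence clause settles discrepancies; silence does not withdraw the protocol's text. The accurate statement is that the analysis is not carried over.
- **Assumed profiles.** A reader might infer that the primary estimate is biased. That holds only if the effect changes with exposure time, and the documents give no evidence of this. The 10-to-30 and 30-to-10 profiles are illustrations.
- **Model form.** The weights come from an identity-link model with equal cells, whereas the SAP specifies logit or log-link models. A logistic simulation with period effects and a different linear profile pointed the same way: against a true average log odds ratio of 0.57, the median estimate was -0.04 for a growing effect and 1.12 for a waning one, while a constant effect was recovered. The bias also depends on period adjustment, which Equations 1-4 include. Without it, the bias would be smaller.
- **Schedule.** The site markings in the SAP's Figure 2 are unreadable here, so the delayed layout is an assumption. If group 6 had no post-transition block, the estimates would be 9.4 and 30.6. That would contradict the SAP's statement of at least 8 weeks at each site, so nothing rests on it.

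The random-slope wording and the derived exposure variables suggest under-specification more than a firm commitment to a constant effect. They still do not supply the missing term.

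**Conclusion.** The omission holds: the protocol plans the interaction, the SAP does not contain it, and Equations 1-4 impose one effect whatever the time since crossover. If the effect does change, the consequence can be material. On the original layout, and on the delayed one as assumed above, the estimate is about 7 points for the rising example and about 33 for the falling one. On the original layout the averages over observed intervention cells are 16.7 and 23.3. These sizes rest on the linear-model approximation, equal cells, period adjustment and the assumed profiles.

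A reader might go further and conclude that the constant-effect model should be replaced as the primary analysis, or that the result should switch estimand if the exposure-time effects appear to differ. The documents do not support either step. A constant effect is estimated without bias, and with 12 clinics the interaction is too imprecise to govern the primary conclusion.

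**What to change.** Keep the constant-effect model as the primary analysis. Add the protocol's analysis to the SAP as a pre-specified secondary or sensitivity analysis, for the primary outcome and for TB diagnosis:

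1. Keep the period terms. Add either a linear term for time since the end of transition or one indicator per exposure block, and choose between them in advance. The linear term is sound only if change is roughly linear.
2. Do not pool blocks 3 and later.
3. Report the effect by exposure time and its average beside the constant-effect estimate. State the weights of the average, for example the observed intervention cells.
4. Describe the constant-effect estimate as assuming an effect that does not change with exposure time.
5. Note that the longest exposures come from the earliest groups only. On the original layout, block 6 is group 1 (2 clinics) and block 5 is groups 1 and 2 (4 clinics).

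The cost is one extra model per outcome on data already collected. The standard error of the average is about 1.35 times that of the constant effect with observed-cell weights and about 1.6 times with equal block weights. Power for the interaction is limited: for a slope of 4 points per block, as in the example, with transition data excluded, it is about 51-60% at n = 11 and 79-87% at n = 22.7. A non-significant interaction should therefore not be read as evidence that the effect is sustained.

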Version 2.0 Update: It was noted above that on 15 October 2022, the President of Uganda announced Ebola-related public health restrictions preventing public movement in two districts where two study sites are located: Mubende and Kasambya. As a result, the principal investigators immediately paused all new introductions of the study intervention according to the schedule noted above. The effects and the duration of this public health emergency are currently unknown, but they may adversely affect both the implementation of this trial and its outcomes. The alternate analysis plans below may become especially relevant if this outbreak invalidates previous assumptions about participant and/or outcome accrual and feasible analytical approaches.

We face a high-level of uncertainty about how the Ebola outbreak and/or other secular trends will affect participant and/or outcome accrual or prior assumptions about sample size and feasible analytical approaches. Accordingly, we lay out our proposed approach below, based on currently available information and our desire to pre-specify the analysis, while recognizing that there may be need to alter these plans if we encounter problems with the analysis, with appropriate justification. The flexibility of our analysis options highlights a strength of the trial design: that is, its pragmatism in the face of an extreme event.

Individual level data will be collapsed at health facility and cluster levels by trial month in both control and intervention exposure periods to create panel data. We will estimate the difference in primary outcome by comparing control and intervention periods using aggregated data. Two models will be considered namely 1) **Random effects logit model (xtlogit)** for binary dependent outcome where the probability of the outcome is determined by the cumulative logit distribution function and accommodates various correlation structures; and 2) **Random effects GEE model (xtreg, re)**; this model accommodates fewer correlation structures than

the former. Both models allow cluster-level aggregated data to vary across time by cluster. The multivariable model will include cluster-level covariates. We will test various correlation structures and choose the final model using likelihood ratio tests and information criteria (AIC, BIC and QIC).

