3.1.2 Populations and subgroups to be analyzed

a. Populations

- **Intention-to-treat (ITT):** The primary analysis will consider the intention-to-treat population, including all index patients eligible at all sites and their identified and screened contacts. Pre-intervention patients in the intention-to-treat population will be those who were diagnosed at a site during the pre-intervention period, and subsequently, their contacts will be considered pre-intervention contacts. Intervention period patients in the ITT population will be those who were diagnosed with TB at a site during the intervention period, and subsequently, their contacts will be considered intervention contacts.
- A per-protocol analysis is not relevant in this case since all community health workers at the site during the intervention period will be exposed to the user-centered implementation strategy, and it is not possible to quantitatively measure adherence to the implementation components in the context of the pragmatic features of the trial.

b. **Adjusted analyses:** In the presence of secular trends (and thus analysis at the individual level), the adjusted analyses will consider age (continuous), sex, HIV status, and any other baseline characteristics found to be imbalanced between control and intervention periods. In the absence of secular trends (and thus aggregated analysis by site and by month), the adjusted analyses will consider covariates such as the proportion of male vs. female, mean age, health center level, health center location (peri-urban vs. rural), and GDP of health center district (low vs. high). Data will be collapsed by the sum of total outcomes for binary outcome variables and mean value for any continuous variables (e.g., age). We will adjust for trial period as appropriate for stepped wedge trial data analysis.

c. **Subgroup analyses:** In the case of individual patient data analysis, five subgroups will be analyzed using the ITT population.

- Age
- Sex: All eligible patients at randomized health centers will be divided into two groups by sex and analyzed separately.

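### The SAP's alternative aggregated analysis names a binary logit and a mislabelled linear model for clinic-month data, and neither is given the number of symptom-positive contacts

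*SAP*

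**What the plan says.** The SAP section Alternative Statistical analyses, presented there as the proposed approach given the uncertainty over Ebola and other secular trends, states: "Individual level data will be collapsed at health facility and cluster levels by trial month". It then estimates the difference in the primary outcome between control and intervention periods from the aggregated data.

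- **First candidate:** xtlogit, "for binary dependent outcome where the probability of the outcome is determined by the cumulative logit distribution function".
- **Second candidate:** "Random effects GEE model (xtreg, re".
- **Applied to:** "Both models allow cluster-level aggregated data to vary across time by cluster".
- **Choice:** "We will test various correlation structures and choose the final model using likelihood ratio tests and information criteria", listed as AIC, BIC and QIC.

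Section 3.1.2, item b (Adjusted analyses), adds: "Data will be collapsed by the sum of total outcomes for binary outcome variables". It links the aggregated route to a condition: "In the absence of secular trends (and thus aggregated analysis by site and by month".

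Three other places bear on this. The Primary Outcome definition divides contacts completing evaluation by contacts screening symptom positive. Statistical Methods names a cluster-period mixed-effects logit. Item c (Intervention Effect Analysis) defines the effect as a ratio and replaces the odds ratio by a proportion ratio, from a modified Poisson model, when the outcome proportion exceeds 15%.

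**The concern.** A clinic-month sum or proportion is not a binary outcome, so the first model does not fit the data it is given. The text names no binomial total, offset or weight for either model. A month with one symptom-positive contact and a month with twenty are not distinguished, and the denominator that defines the primary outcome drops out.

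This matters here because the strategy is built to change that denominator. A contact identification tool is one of its components, and the sample size section projects that enrolment may exceed plan four-fold or more if the strategy is highly effective. An analysis without the denominator can mistake more contacts for better completion.

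The second model is a linear random-effects model, not a GEE. Its effect is a risk difference, whereas item c specifies a ratio. The two candidates therefore answer different questions, and the SAP does not say which would give the primary result.

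**Working it through.** **Cell size.** The SAP's planning figures are m = 1 symptomatic contact per index patient, g = 11 index patients per clinic per 8 weeks, T = 7 periods and K = 12 clinics. N = m × g × T × K = 1 × 11 × 7 × 12 = 924, as the SAP states. No stated figure is disputed here. Eleven contacts per 8-week block is 11 / 2 = 5.5 per clinic-month.

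**Assumption for the logit.** The collapsed value is read as zero or non-zero. The SAP does not say this. The modelled quantity is then P(any) = 1 − P(0).

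**Formula.** With correlation ρ between contacts in a clinic-month, a beta-binomial gives

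P(0) = Γ(β+n) Γ(α+β) / [Γ(β) Γ(α+β+n)], where α = p(1−ρ)/ρ and β = (1−p)(1−ρ)/ρ.

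At ρ = 0.172, (1−ρ)/ρ = 4.814. So α = 0.963 and β = 3.851 at p = 0.20, and α = 1.926 and β = 2.888 at p = 0.40. The correct marginal odds ratio for 0.20 to 0.40 is (0.4/0.6)/(0.2/0.8) = 2.67.

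| Scenario, ρ = 0.172 | P(any), control | P(any), intervention | OR obtained | Correct OR |
|---|---|---|---|---|
| 0.20 to 0.40, n = 5.5 | 0.575 | 0.849 | 4.1 | 2.67 |
| 0.20 to 0.40, n = 11 | 0.728 | 0.940 | 5.9 | 2.67 |
| 0.20 to 0.20, n = 5.5 to 11 | 0.575 | 0.728 | 2.0 | 1.00 |
| 0.20 to 0.20, n = 5.5 to 22 | 0.575 | 0.841 | 3.9 | 1.00 |

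A lower ICC makes the distortion larger. At the protocol's clinic ICC of 0.043, the same formula gives 5.5 for the first row and 13.2 for the second.

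**Fitted models.** Trials were simulated with 12 clinics, 16 months, transition months dropped, Poisson monthly counts averaging 5.5, high-volume clinics three times low-volume ones, and ICC 0.172 on the latent scale (150 to 200 trials per scenario). Odds ratios here are conditional on clinic, so they differ from the marginal values above.

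| Scenario | True OR | Events/trials logit, median OR | Any/none logit, median OR | Linear model, mean risk difference |
|---|---|---|---|---|
| 0.20 to 0.40 | 2.98 | 3.03 | 3.95 | 0.202 |
| 0.20 to 0.20, same volume | 1.00 | 1.02 | 0.95 (4% reject) | 0.001 (5% reject) |
| 0.20 to 0.20, two-fold volume | 1.00 | 1.01 | 2.90 (69% reject) | −0.002 (5% reject) |
| 0.20 to 0.20, four-fold volume | 1.00 | 1.04 | 10.9 (100% reject) | 0.004 (7% reject) |

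The any/none logit keeps its error rate when volume is constant and loses it when volume rises with the intervention. The linear model stays close to the true risk difference throughout.

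**Ranking the two models.** In the first scenario the median −2 log-likelihood was 168 for the any/none logit and 3 for the linear model fitted by maximum likelihood, so AIC chose the linear model in every run. There were 12 × 14 = 168 clinic-months, about 163 of them non-empty. Recording the proportion in percent adds 2 × 163 × ln(100) ≈ 1,501 to the linear value and reverses the choice. A ranking that depends on the units carries no information. QIC is a quasi-likelihood criterion, and a generalised least squares random-effects fit has no likelihood to compare.

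**The case against.** The strongest reply is that the SAP already has a main model. Statistical Methods and item c name a mixed-effects logit and a modified Poisson, and the two models at issue sit under an Alternative heading tied mainly to Ebola. A reader might infer from section 3.1.2 that they become the default whenever no secular trend is found. The text does not go that far: that sentence lists covariates for adjusted analyses and names neither command. It does prescribe aggregation in that case, and it does not say which model then applies. The protocol's multilevel logistic model does not settle this, because the SAP takes precedence.

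The zero/non-zero reading is also not in the SAP. The outcome definition is a proportion, and item c says proportions will be calculated for each site and cluster. This stands: the odds ratios above show what an unstated step could do, not what the team has said it will do.

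Other stronger readings do not hold:

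- **Larger odds ratios.** Without clustering, P(any) = 1 − (1−p)^n gives 6.5 at 5.5 contacts and 25.8 at 11. The SAP assumes a clinic ICC of 0.172, so these do not describe its setting.
- **Both models grossly wrong.** The linear model is not. That it is unweighted is inferred from silence.
- **The logit fails at 0 or 1.** That applies to transforming observed proportions. A random-effects logit models the probability.
- **The selection rule invalidates the primary p-value.** The sentence can mean choosing a correlation structure within each model, and its criteria are fit statistics, not the effect estimate. No such damage was quantified.

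**Conclusion.** The point holds in limited form. As written, the alternative aggregated analysis pairs a binary-outcome model with data that are not binary, mislabels a linear model as a GEE, and does not bring the symptom-positive denominator into either. It also leaves open which model and which effect measure would give the primary result.

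The size is conditional. If collapsed values are read as zero or non-zero, the marginal odds ratio for 20% to 40% is about 4.1 (5.5 contacts per clinic-month) to 5.9 (11 contacts) instead of 2.67, at ICC 0.172. A volume rise alone gives about 2.0 at two-fold and 3.9 at four-fold. The SAP's four-fold projection concerns enrolment against plan, so using it as an intervention-to-control ratio is an assumption. The linear branch has an estimand problem and an unstated weighting, not a material bias. The objection to LRT, AIC, BIC and QIC applies only if they are meant to rank the two models against each other.

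**What to change.** For any aggregated analysis, model completed and symptom-positive contacts per clinic-period, with a clinic random effect and period effects. Use either an events/trials binomial mixed model or a log-link Poisson with the log of symptom-positive contacts as offset. The second keeps the proportion ratio of item c. Choose one of these and name it as primary before the data are analysed.

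Then:

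- remove xtlogit on collapsed data;
- correct the GEE label on xtreg, re, state its weighting, and keep it only as a sensitivity analysis;
- limit likelihood ratio tests and information criteria to correlation structures within one model family;
- state in section 3.1.2 which model applies when the data are aggregated.

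The cost is minor SAP rewording and giving up the choice of model after the data are seen. No new data are needed, because the outcome definition already requires both counts.
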